1. SYNOPSIS

Protocol Title: Randomized, Double-Blind, Placebo-Controlled, Parallel-Group Study to Assess the Safety, Tolerability, and Efficacy of BIIB092 in Subjects with Mild Cognitive Impairment due to Alzheimer's Disease or with Mild Alzheimer's Disease

Protocol Number: 251AD201

Version Number: 4

Name of Study Treatment: BIIB092 (formerly known as BMS 986168, IPN007)

Study Phase: 2

Study Indication: Mild cognitive impairment (MCI) due to Alzheimer's disease (AD) or mild AD

Study Rationale: BIIB092 is a humanized immunoglobulin G4 monoclonal antibody that has been shown to bind tau at the amino terminus. Although tau is primarily an intracellular protein, a portion of tau is secreted by neurons as N-terminal tau fragments.

BIIB092 has been shown to lower cerebrospinal fluid (CSF) concentrations of N-terminal tau in nonclinical studies, a single-ascending-dose study in healthy participants, and a multiple-ascending-dose study in participants with progressive supranuclear palsy. Based upon the close links between tau pathology, neurodegeneration, and clinical features consistent with AD, coupled with the evidence that tau pathology can spread via neuronal release and uptake of pathological tau species, examination of BIIB092 in the clinical AD setting is strongly supported as a potential disease-modifying therapy. This study will assess the safety and efficacy of BIIB092 in participants with MCI due to AD or with mild AD and help to inform on dose selection in this patient population.

Study Objectives and Endpoints: **Placebo-Controlled Period**

The primary objective of the study for the placebo-controlled period is to evaluate the safety and tolerability of BIIB092 in participants with MCI due to AD or with mild AD.

The primary safety endpoints that relate to this objective are the incidence of adverse events (AEs) and serious AEs (SAEs) during the

CONFIDENTIAL

The information contained herein may not be used, disclosed, or published without the written consent of Biogen MA Inc.

placebo-controlled period.

Secondary objectives and endpoints are as follows:

- To evaluate the efficacy of multiple doses of BIIB092 in slowing cognitive and functional impairment in participants with MCI due to AD or with mild AD as measured by the change from Baseline over time at Week 78 on the Clinical Dementia Rating Scale (CDR) - Sum of Boxes (CDR-SB). This is the primary efficacy objective, with the primary efficacy endpoint.
- To evaluate the immunogenicity of BIIB092 after multiple doses in participants with MCI due to AD or with mild AD as measured by the incidence of anti-BIIB092 antibodies in serum over time up to Week 90.

Exploratory objectives and endpoints are as follows:

- To assess the effect of BIIB092 on the clinical progression of AD as measured by changes from Baseline over time up to Week 78 on the Mini-Mental State Examination (MMSE), International Shopping List Test Immediate Recall (ISLT), Category Fluency and Letter Fluency tests from the Delis-Kaplan Executive Function System (DKEFS), Digit Symbol Substitution Test (DSST), Trail Making Test Part A (Trails A), Everyday Cognition (eCog), Alzheimer's Disease Cooperative Study-Activities of Daily Living (ADCS-ADL), Functional Activities Questionnaire (FAQ), Alzheimer's Disease Assessment Scale-Cognitive (ADAS-Cog 13 [13 item]), and Neuropsychiatric Inventory-10 (NPI-10).
- To assess the effect of BIIB092 on changes in caregiver burden and participant quality of life as measured by changes from Baseline over time up to Week 68 on the Zarit Burden Interview (ZBI) and Quality of Life for Alzheimer's Disease (QoL-AD).
- To assess the effect of BIIB092 on resource utilization as measured by the Resource Utilization in Dementia-Lite (RUD-Lite) Version results over time up to Week 68.
- To assess BIIB092 pharmacokinetics (PK) in serum (trough serum BIIB092 concentrations and end-of-infusion serum BIIB092 concentrations) from the samples collected at the

CONFIDENTIAL

The information contained herein may not be used, disclosed, or published without the written consent of Biogen MA Inc.

visits indicated in the Schedule of Activities in participants with MCI due to AD or with mild AD.

- [REDACTED]
- [REDACTED]
- To assess the effect of BIIB092 on biomarkers in blood as measured by changes from Baseline over time up to Week 76 on blood levels of disease-related biomarkers, including but not limited to, tau and other markers of neurodegenerative disease.
- [REDACTED]
- [REDACTED]
- To assess the effect of BIIB092 on brain structure as measured by changes from Baseline over time up to Week 78 on magnetic resonance imaging (MRI) morphometric measures, including volume and cortical thickness of certain brain areas.

Long-Term Extension Period

The primary objective for the long-term extension (LTE) period is to evaluate the long-term safety and tolerability of BIIB092 in participants with MCI due to AD or with mild AD.

The primary safety endpoint that relates to this objective is the

CONFIDENTIAL

The information contained herein may not be used, disclosed, or published without the written consent of Biogen MA Inc.

incidence of AEs and SAEs over the placebo-controlled period and LTE period of the study.

Exploratory objectives and endpoints are as follows:

- To further evaluate the immunogenicity of BIIB092 after multiple doses in participants with MCI due to AD or with mild AD as measured by the incidence of anti-BIIB092 antibodies in serum over time up to Week 238.
- To further assess the effect of BIIB092 on disease progression as measured by fluid and radiological biomarkers, as well as additional clinical and health outcomes as measured by the following:
 - Changes over the placebo-controlled period and LTE period on the CDR-SB, MMSE, ISLT, Category Fluency and Letter Fluency tests from the DKEFS, DSST, Trails A, eCog, ADCS-ADL, FAQ, ADAS-Cog-13 (13-item), and NPI-10
 - Changes over the placebo-controlled period and LTE period on the ZBI, QoL-AD, and RUD-Lite
 - [REDACTED]
 - Changes over the placebo-controlled period and LTE period on [REDACTED] MRI brain morphometric measures
- To assess BIIB092 PK in serum (trough serum BIIB092 concentrations) [REDACTED] from the samples collected at the visits indicated in the Schedule of Activities in participants with MCI due to AD or with mild AD.

Study Design:

This is a Phase 2, randomized, double-blind, placebo-controlled, parallel-group study consisting of a double-blind, placebo-controlled period and an LTE period.

[REDACTED]

CONFIDENTIAL

The information contained herein may not be used, disclosed, or published without the written consent of Biogen MA Inc.

- Study Location:** Approximately 100 study sites globally are planned.
- Number of Planned Participants:** Approximately 528 participants were planned to be randomized. Due to fast recruitment, the study was over-enrolled and 654 participants have been randomized.
- Study Population:** This study will be conducted in participants aged 50 to 80 years, inclusive, with MCI due to AD or mild AD according to National Institute on Aging-Alzheimer's Association criteria. [REDACTED]
- [REDACTED] Participants must also perform at 1 standard deviation below the age-adjusted normative mean on either the ISLT or the International Shopping List Test Delayed Recall and have a CDR global score of 0.5 for MCI due to AD or 0.5 or 1 for mild AD, an MMSE score of 22 to 30 (inclusive), and a CDR Memory Box score of ≥ 0.5 .
- Detailed eligibility criteria are described in Section 8.
- Treatment Groups:** During the placebo-controlled period, randomized participants will receive 1 of the following study treatments by intravenous (IV) infusion, starting on Study Day 1:
- low-dose BIIB092 - 125 mg once every 4 weeks or 375 mg once every 12 weeks (88 participants planned in total, 44 per regimen)
 - medium-dose BIIB092 - 600 mg once every 4 weeks (88 participants planned)
 - high-dose BIIB092 - 2000 mg once every 4 weeks (176 participants planned)
 - placebo (176 participants planned)

CONFIDENTIAL

The information contained herein may not be used, disclosed, or published without the written consent of Biogen MA Inc.

During the dose-blinded LTE period, participants will receive BIIB092 by IV once every 4 weeks beginning at Week 80. Participants who were randomized to receive BIIB092 during the placebo-controlled period will continue to receive BIIB092 at the dose they were randomly assigned. Participants randomized to receive placebo during the placebo-controlled period will receive BIIB092 at the high dose (2000 mg) once every 4 weeks during the LTE period.

Duration of
Treatment and
Follow-up:

The total duration for participants who complete the placebo-controlled period and do not enter the LTE period will be approximately 99 weeks. For participants who complete both the placebo-controlled period and the LTE period, the total study duration will be approximately 247 weeks.

Placebo-Controlled Period

Participation in the placebo-controlled period will be approximately 99 weeks, which includes the Screening Period of approximately 9 weeks, the 76-week Treatment Period, and the End-of-Study (EOS) Visit at Week 78, and for participants not entering the LTE period, a Follow-up Safety Visit at Week 90, or approximately 14 weeks after the last dose of study treatment. It is recommended that all the screening procedures be completed within 65 days; however, the overall Screening Period may be extended up to 90 days in consultation with the Medical Monitor in advance and provided that written documentation is received from the Sponsor or delegate [REDACTED]. Participants will have approximately 25 outpatient clinic visits:

- Participant eligibility will be determined at up to 3 visits during the Screening Period (Screening Visits 1, 2, and 3).
- On Study Day 1, eligible participants will be randomized, have scheduled assessments per the Schedule of Activities, and receive the first infusion of randomized study treatment.
- Participants will return to the clinic at 4-week intervals during the Treatment Period for infusions of study treatment and study assessments (Weeks 4, 8, 12, 16, 20, 24, 28, 32, 36, 40, 44, 48, 52, 56, 60, 64, 68, 72, and 76). The last dose of study treatment will be administered at Week 76 (End-of-Treatment Visit).
- For a participant who completes the Treatment Period at Week 76, there will be an EOS Visit at Week 78 for final

CONFIDENTIAL

The information contained herein may not be used, disclosed, or published without the written consent of Biogen MA Inc.

study assessments of the placebo-controlled period. A Follow-up Safety Visit will occur at Week 90 (14 weeks after the last dose of study treatment is administered), unless the participant elects to enter an extension study following the Week 78 Visit.

- Participants who discontinue study treatment prematurely will be asked to remain in the study and continue all protocol-specified visits and procedures. These participants should be encouraged to attend at least the Week 24, Week 52, and Week 78 visits, depending on when treatment was discontinued, and undergo all the scheduled procedures. At a minimum, these visits should include assessment of AEs/SAEs and concomitant medications and key clinical assessments, including at least the CDR, MMSE, ISLT, ADAS-Cog 13, ADCS-ADL, and FAQ. Participants who discontinue study treatment prematurely will also be asked to return to the study site for a Follow-up Safety Visit 14 weeks after receiving the last dose of study treatment.
- Participants who withdraw from the study prematurely are to return to the study site for an Early Termination (ET) Visit and assessments and for the Follow-up Safety Visit 14 weeks after administration of the final infusion of study treatment.

Long-Term Extension Period

Participants who meet the LTE inclusion and exclusion criteria will be eligible to enter the dose-blinded LTE period, which includes the LTE Screening Period of approximately 4 weeks starting at Week 76, the 144-week Treatment Period starting at Week 80, the EOS Visit at Week 226, and the Follow-up Visit at Week 238.

Participants will have approximately 39 outpatient clinic visits during the LTE period:

- Participant eligibility will be determined at Week 76 or Week 78 of the placebo-controlled period and confirmed at Week 80 of the LTE period.
- At the Week 80 Visit, eligible participants will have scheduled assessments per the Schedule of Activities and receive the first infusion of BIIB092 during the LTE period.

CONFIDENTIAL

The information contained herein may not be used, disclosed, or published without the written consent of Biogen MA Inc.

All participants receiving placebo in the placebo-controlled period will receive BIIB092 at the high dose (2000 mg) once every 4 weeks during the LTE period.

- Participants will return to the clinic at 4-week intervals during the Treatment Period for infusions of study treatment and study assessments.
- The last dose of study treatment will be administered at Week 224 (End-of-Treatment Visit). The EOS Visit will occur at Week 226 and the Follow-up Visit at Week 238.
 - Participants who discontinue study treatment prematurely will be asked to remain in the study and continue all protocol-specified visits and procedures. These participants should be encouraged to attend at least the Week 80, 104, 116, 128, 152, 156, 176, 196, 200, 224, and 226 Visits, depending on when treatment was discontinued, and undergo all the scheduled procedures. At a minimum, these visits should include assessment of AEs/SAEs and concomitant medications and key clinical assessments, including at least the CDR, MMSE, ISLT, ADAS-Cog 13, ADCS-ADL, and FAQ. Participants who discontinue study treatment prematurely will also be asked to return to the study site for a Follow-up Safety Visit 14 weeks after receiving the last dose of study treatment.
 - Participants who withdraw from the study prematurely are to return to the study site for an Early Termination Visit and assessments and for the Follow-up Safety Visit 14 weeks after receiving the last dose of study treatment.

CONFIDENTIAL

The information contained herein may not be used, disclosed, or published without the written consent of Biogen MA Inc.

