10. DISCONTINUATION OF STUDY TREATMENT AND WITHDRAWAL OF PARTICIPANTS FROM THE STUDY

10.1. Discontinuation of Study Treatment

A participant must permanently discontinue study treatment for any of the following reasons:

- The participant becomes pregnant. Study treatment must be discontinued immediately, and the pregnancy must be reported according to the instructions in Section 15.4.1.
- The participant withdraws consent to continue study treatment.
- The participant experiences a medical emergency that necessitates permanent discontinuation of study treatment or unblinding of the participant's treatment assignment.
- The participant experiences an AE or SAE that does not resolve or requires continued treatment that meets exclusionary criteria.
- The participant experiences a severe infusion reaction
- At the discretion of the Investigator for medical reasons.
- At the discretion of the Investigator or the Sponsor for noncompliance with the terms of the protocol.

The primary reason for discontinuation of study treatment must be recorded in the participant's case report form (CRF).

All participants who discontinue study treatment prematurely will be asked to remain in the study and continue all protocol-specified visits and procedures for the period in which they discontinued treatment (i.e., placebo-controlled or LTE). Participants who discontinue treatment during the placebo-controlled period should be encouraged to attend at least the Week 24, Week 52, and Week 78/EOS Visits and who discontinue treatment during the LTE should be encouraged to attend at least the Week 80, 104, 116, 128, 152, 156, 176, 196, 200, 224, and 226/EOS Visits, depending on when treatment was discontinued, and undergo all the scheduled procedures. At a minimum, these visits should include assessment of AEs/SAEs and concomitant medications and key clinical assessments, including at least the CDR, MMSE, ISLT, ADAS-Cog 13, ADCS-ADL, and FAQ. Participants who discontinue study treatment prematurely, regardless of the treatment period, will be asked to return to the study site for a Follow-up Safety Visit 14 weeks after receiving the last dose of study treatment. See [Table 1](#), [Table 2](#), [Table 3](#), and [Table 4](#) for the Schedule of Activities.

CONFIDENTIAL

The information contained herein may not be used, disclosed, or published without the written consent of Biogen MA Inc.

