15.3. Monitoring and Recording Events

15.3.1. Adverse Events

Any AE experienced by the participant between the time of first dose of study treatment and the participant’s final clinic visit (including the Follow-up Safety Visit) is to be recorded on the CRF, regardless of the severity of the event or its relationship to study treatment, [REDACTED]

[REDACTED] At each study visit, the Investigator will assess the participant for AEs and will record any new AEs or updates to previously reported AEs on the CRF.

AEs that are ongoing when the participant completes or discontinues the study will be followed by the Investigator until the event has resolved, stabilized, or returned to baseline status. AE outcome will be recorded on the CRF, as applicable.

CONFIDENTIAL

The information contained herein may not be used, disclosed, or published without the written consent of Biogen MA Inc.

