16.3.2. Methods of Analysis

16.3.2.1. Adverse Events

All analyses of AEs will be based on the principle of treatment emergence. An AE is considered to be treatment emergent if it has an onset date on or after the date of first dosing, or if it was

CONFIDENTIAL

The information contained herein may not be used, disclosed, or published without the written consent of Biogen MA Inc.

present prior to the first dose and subsequently worsened. The incidence of all AEs will be presented by system organ class and preferred term by dose group and for the overall active treatment group. In addition, the incidence of all AEs will be presented by severity, by relationship to study treatment, [REDACTED].

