3.2 Analyses Period

Depending on the purpose, different analyses will be conducted on the following study periods:

1. LTE period. Only data in the LTE period will be included in these analyses. This LTE analysis period will be applied to all the AE analyses, and the analyses will include all subjects who were dosed in the LTE period.
2. Placebo-controlled and LTE period. All the data in the placebo-controlled and LTE periods will be included in these analyses. This analysis period will be applied to analyses including, but not limited to all efficacy analyses and listings. The analyses will include all subjects who were dosed in the study including those who did not enroll into the LTE period. For example, line plot of CDR sum of box mean change from baseline over time. in the placebo-controlled and LTE period.
3. Placebo-controlled and LTE active treatment period. Active treatment period is defined as the study period(s) that a subject received BIIB092. For early start subjects – subjects who received BIIB092 in both placebo-controlled and LTE period, all the data (placebo-controlled and LTE periods) will be included in the analyses. For late start subjects – subjects who received placebo in the Placebo-controlled period and BIIB092 in the LTE period, only data in the LTE period will be included. This analysis period will be applied to majority of safety tables, and the analyses will include all subjects who were dosed in the study except for subjects who received only placebo in the placebo-controlled period and did not get dosed in the LTE period. An example is the incidence rate of adverse events in the placebo-controlled and LTE active treatment period.

Subjects to be included in a certain output is determined by both the analysis set and the analysis period. For example, the incidence table of adverse events in the LTE period will include subjects in the safety population for the LTE period, i.e., all randomized subjects who received at least one dose of study treatment in the LTE period. The incidence rate table of adverse events in the placebo-controlled and LTE active treatment period will include subjects in the safety population for the active treatment period, i.e., all randomized subjects who received at least one dose of study treatment in the active treatment period. In this SAP we do not separately define the analysis set in each analysis period.

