5.4.1.3 Incidence, Incidence Proportion and Incidence Rate

- Incidence and incidence proportion will be provided in incidence proportion tables. Incidence is defined as the number of subjects who experienced an event. Incidence proportion is defined as the number of subjects who experienced an event divided by total number of subjects in the analysis population, i.e., percentage. Each subject will be counted only once within each category.
- Incidence and incidence rate will be provided in incidence rate tables. Incidence rate of an event based on the entire follow-up time – defined as the number of subjects who experienced an event divided by the total of entire follow-up time among the subjects in the analysis set (e.g., incidence rate per 100 subject-years). The entire follow-up time for a subject (subject-years) is defined as the sum of all subjects' follow-up time, where a subject's follow-up time is calculated as the number of days (inclusive) from first dose of study drug until the last day on study, divided by 365.25. Each subject will be counted only once within each category.

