5.4.2 Clinical Adverse Events

Treatment-emergent AEs (TEAE)

A treatment-emergent AE is defined as AE that started or worsened after the start of first infusion of study treatment in LTE period.

First dose for below definitions is the first dose in LTE period

To define treatment emergence for AEs with missing start or stop date or time the following additional criteria will be used:

- if both the start and stop dates for a particular AE are missing, then that AE is considered treatment emergent;
- if the start date for a particular AE is missing and the stop date/time falls after the first dose date/time, then that AE is considered treatment emergent;
- if the start date for a particular AE was the same as the first dose date, and the start time was missing and stop time is after the first dose or missing, then that event is considered treatment emergent.

For AEs with a partial start date, the following imputation method will be used to determine if the event is treatment emergent:

- When only the day is missing, and the year/month is equal to the year/month of first dose date, and the AE stop date is missing or on/after the first dose date, then use the first dose date as AE start date. Otherwise impute the AE start date as the first day (1) of the AE start month
- When the AE start month is missing, and the year equals to the year of first dose date, and the AE stop date is missing or on/after the first dose date, then use the first dose date as AE start date. Otherwise impute the AE start date as the first day (01January) of the AE start year

CONFIDENTIAL

The information contained herein may not be used, disclosed, or published without the written consent of Biogen MA Inc.

	Statistical Analysis Plan Long-Term Extension Period	V1.0
---	---	-------------

For AEs with a partial end date, the following imputation method will be used:

- When only the day is missing, and the year/month equal to the year/month of the last date on study, then use the last date on study as AE stop date. Otherwise impute the AE stop date as the last day of the AE stop month
- When the AE stop month is missing, and the year equals to the year of last date on study, then use the last date on study as AE stop date. Otherwise impute the AE stop date as the last day (31December) of the AE stop year

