5.4.2.2 Incidence Rate Analysis

Incidence rate of AEs based on the entire follow-up time for subjects with at least 1 AE in LTE period may be summarized by system organ class and preferred terms. The incidence rate tables will be presented by LTE treatment group. The entire follow-up time for LTE period is from the first dose in LTE period until the last day on study.

Follow-up adjusted incidence rate of AEs may also be summarized for placebo-controlled and LTE active treatment period, due to the different length of placebo-controlled and LTE active treatment period in early start versus late start high-dose BIIB002 subjects. The entire follow-up time is from the first dose in active treatment period (placebo-controlled period first dose of BIIB092 for early start subjects and LTE period first dose of BIIB092 for late start subjects) until the last day in the study.

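### The LTE SAP's active-treatment AE rates count time and events to the last day on study, with no companion cut tied to the last BIIB092 dose; the dilution is modest and cheap to show

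*Protocol*

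**What the plan says.** **Retention.** Protocol Synopsis: "Participants who discontinue study treatment prematurely will be asked to remain in the study and continue all protocol-specified visits and procedures". Protocol 10.1 limits this to "procedures for the period in which they discontinued treatment (i.e., placebo-controlled or LTE"), so a person who stops in the placebo-controlled period is followed to Week 78 and one who stops in the LTE to Week 226. Protocol 15.3.1 has sites record "Any AE experienced by the participant between the time of first dose of study treatment and the" participant's final clinic visit.

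**Treatment emergence.** Both definitions give a start only. Protocol 16.3.2.1: "An AE is considered to be treatment emergent if it has an onset date on or after the date of first dosing". SAP 5.4.2: "A treatment-emergent AE is defined as AE that started or worsened after the start of first infusion of study treatment in LTE period".

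**Period.** SAP 3.2: "Active treatment period is defined as the study period(s) that a subject received BIIB092". The period follows study periods rather than dosing dates, and early-start participants contribute everything from both.

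**Person-time.** SAP 5.4.1.3 counts days "from first dose of study drug until the last day on study". SAP 5.4.2.2 repeats this for the active treatment period, "until the last day in the study", and gives as its reason that early and late starters have active periods of different length.

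**Tables affected.** Nine of the AE and SAE tables listed in SAP 5.4.2.1 are starred for presentation as rates over this period. That section says they will be presented; 5.4.2.2 says they may be.

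**Exposure.** SAP 5.2.4 computes weeks on BIIB092 from first to last dose.

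**The concern.** A rate adjusted for the length of the active treatment period should reflect time at risk on drug, or shortly after it. Under these definitions a participant who stops early and stays contributes months of drug-free time, and any background events in that time, to a BIIB092 column. If drug raises an event rate only while it is given, the tabulated rate is pulled toward background. The pull is strongest in the group with the most stopping, so comparisons between doses, and between early and late start, can be distorted unequally.

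The efficacy section (SAP 5.3.3) names treatment discontinuation as an intercurrent event and chooses a treatment-policy strategy. The safety sections of the supplied SAP state no such choice, give no cut-off relative to last dose and plan no on-treatment version.

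**Working it through.** The plan gives no figure for off-drug time, so there is none to reproduce. Its visit arithmetic does hold: Week 76 + 14 = Week 90, (631 − 533)/7 = 14 weeks; Week 224 + 14 = Week 238, (1667 − 1569)/7 = 14 weeks.

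**1. One participant.** SAP person-time = end day − first dose day + 1. The comparison caps the end day at last dose + 98 days (14 weeks).

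| Case | SAP rule (days) | Capped (days) | Beyond cap |
|---|---|---|---|
| One dose on Day 1, followed to Week 78 (Day 547) | 547 | 99 | 448/547 = 82% |
| Last dose Week 24 (Day 169), followed to Week 78 | 547 | 267 | 280/547 = 51% |
| One dose at Week 80 (Day 561), followed to Week 104 (Day 729) | 169 | 99 | 70/169 = 41% |
| One dose at Week 80, followed to Week 128 (Day 897) | 337 | 99 | 238/337 = 71% |

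**2. A treatment group, placebo-controlled period.** Assume a fraction p stops, with last dose uniform on 0 to 76 weeks, and all stay to Week 78. Time beyond the cap is positive only for stops before Week 64, so:

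- mean per stopper = 64²/(2 × 76) = 26.9 weeks
- share of person-time f = p × 26.9/78
- p = 10%, 20%, 30% gives f = 3.5%, 6.9%, 10.4%

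Counting stops at the 19 infusions before the last, instead of continuously, gives 3.7%, 7.3%, 11.0%. If half of the stoppers stay and the rest leave at last dose + 14 weeks, that count gives 1.9%, 3.8%, 5.8%.

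**3. Full-length LTE.** Stops uniform on 0 to 144 weeks, follow-up 146 weeks (Week 80 to Week 226): 132²/(2 × 144) = 60.5 weeks per stopper, and f = p × 60.5/146 = 4.1%, 8.3%, 12.4%. SAP 5.6.2 records that no subject reached Week 226, so these are ceilings.

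**4. Shortened LTE, as an illustration.** SAP 5.2.4's top infusion category is 21–26, and Protocol 11.1.1 gives 20 infusions in the placebo-controlled period. That suggests about 6 LTE infusions for early starters, which is an inference. With stops uniform on 0 to 20 weeks and follow-up to 24: 10²/(2 × 20) = 2.5 weeks per stopper, and f = p × 2.5/24 = 1.0%, 2.1%, 3.1%.

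**5. Effect on a rate.** Let the rate be b + e on drug and within 14 weeks of last dose, and b afterwards. The all-follow-up rate is (1 − f)(b + e) + f·b = b + (1 − f)e, so the excess e is understated by the fraction f. This is approximate, because the SAP divides the number of subjects with an event, not the number of events, by total follow-up. If one group had 30% stopping and another 10%, the understatement would differ by 10.4% − 3.5% = 6.9 percentage points; those rates are also assumed.

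**The case against.** The strongest reply is that all-follow-up reporting is legitimate. SAP 5.4.1.3 and 5.4.2.2 describe the rates as based on entire follow-up time, and cutting at last dose plus an interval can introduce informative censoring. This stands, and is why the existing tables should remain.

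Several stronger conclusions that a reader might draw are not supported:

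- *The primary endpoint is diluted.* It is not. Protocol 6 and SAP 2.1 define it as incidence of AEs and SAEs, which SAP 5.4.1.3 expresses as a number of subjects or a proportion. Longer follow-up can only add events to it.
- *Follow-up has no end, or off-drug time is counted as exposure.* Follow-up ends at the last day on study, and the exposure table stops at last dose. What is missing is an end tied to last dose in the rate tables.
- *The protocol treats 14 weeks as the limit of drug effect.* It is the timing of the Follow-up Safety Visit. Protocol 15.3.3 asks for related SAEs after the final visit, and 15.5 uses a longer interval after last dose for contraception.
- *A tolerability signal is hidden.* SAP 5.4.2.1 tabulates AEs leading to interruption, discontinuation and withdrawal for the LTE period, and 5.2.1 and 5.4.2.3 cover reasons for stopping and infusion reactions. Early intolerance would be visible there.

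The stopping rates above have no source. The 20% in Protocol 16.10 is study dropout for the power calculation, not stopping drug while staying in follow-up. The separate placebo-controlled SAP is not among the documents and may hold further rules, but the LTE SAP states its own rule for these tables.

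**Conclusion.** The point holds for the AE and SAE rate tables over the combined active treatment period: no cut-off relative to last BIIB092 dose applies to events or person-time, and the supplied SAP plans no on-treatment companion.

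The effect is large for an individual early stopper but modest for a group: about 3.5% to 10% of placebo-controlled person-time if 10% to 30% stop uniformly and all stay, and about half that if half stay. For early starters the pooled table's share is a weighted mean of the shares in the two periods. The LTE share is below the 4% to 12% ceiling and may be only a few percent. A drug-related excess confined to on-drug time and the following 14 weeks would be blunted by about the same percentages. If the effect outlasts 14 weeks, the blunting is smaller. None of this shows that the planned safety conclusions would be wrong; it supports an inexpensive addition.

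**What to change.** In SAP 5.4.1.3 and 5.4.2.2:

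- Keep the present rates and label them as all-follow-up (treatment-policy) rates.
- Add the nine starred AE and SAE rate tables with numerator and denominator both cut at the earlier of last BIIB092 dose + 14 weeks and last day on study.
- State that 14 weeks is an analysis convention borrowed from the Follow-up Safety Visit, not a limit of drug effect.
- Settle whether the rate tables will or may be produced. Also say when treatment emergence starts for early starters in the combined period, since 5.4.2 anchors it to the first LTE infusion while 5.4.2.2 starts their person-time at the first placebo-controlled-period dose.

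The cost is SAP wording and one extra set of tables from dates already collected, with no change to study conduct. The on-treatment version will have slightly fewer events and may be affected by informative censoring, so it should be read beside the all-follow-up version and not replace it.
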